9.3.3. Other Safety Assessments

The safety and tolerability of rivaroxaban will also be evaluated by assessing other adverse events and clinical laboratory test values.

Any clinically relevant changes, including laboratory reports, occurring during the study must be recorded on the Adverse Event section of the eCRF. Any clinically significant abnormalities persisting at the end of the study/early withdrawal will be followed by the investigator until resolution or until a clinically stable endpoint is reached.

The study includes the evaluations of safety and tolerability according to the time points provided in the Time and Events Schedule.

Adverse Events

Adverse events will be reported by the parents/legally acceptable representatives for the duration of the study up to the Follow-Up Contact (30-days after last dose). Adverse events will be followed by the investigator as specified in Section 12, Adverse Event Reporting.

Clinical Laboratory Tests

The following tests results with reference ranges will be obtained at the visits specified in the Time and Events Schedule. Either hospital laboratory/local laboratory results or central laboratory results are acceptable at the time of study screening period. A central laboratory will be used during the rest of the study:

- Hematology Panel
 - hemoglobin
 - hematocrit
 - red blood cell (RBC) count^a
 - white blood cell (WBC)^b count
 - WBC differential^b:
 - neutrophils
 - lymphocytes
 - monocytes
 - eosinophils
 - basophils
 - platelet count
- Serum chemistry
 - creatinine (eGFR will be calculated using the original or the modified Schwartz formula for pediatric population, see [Attachment 3](#))²⁹
 - liver function tests (ALT, aspartate aminotransferase [AST], total and direct bilirubin, alkaline phosphatase)
- PT, aPTT tests

^a A RBC evaluation may include abnormalities in RBC count and/or RBC parameters (eg, reticulocyte count) and/or RBC morphology, which will then be reported by the laboratory

^b A WBC evaluation may include any abnormal cells, which will then be reported by the laboratory. In addition, any other abnormal cells in a blood smear will also be reported.

9.4. Efficacy Evaluations/Outcomes

The primary efficacy outcome will be any thrombotic event (venous or arterial), defined as:

- The appearance of a new thrombotic burden within the cardiovascular system on either routine surveillance or clinically indicated imaging, or
- The occurrence of a clinical event known to be strongly associated with thrombus (such as cardioembolic stroke, pulmonary embolism).

Subjects who develop either a symptomatic or asymptomatic thrombotic event during the study must permanently discontinue the study drug. All thrombotic events and the primary cause of any death will be adjudicated by the CIAC. Transthoracic echocardiograms will be centrally read by an echocardiographic core laboratory. All available imaging results (eg, transthoracic or transesophageal echocardiograms, or MRIs), should be sent to the CIAC. Sites will be required to complete a worksheet, compile an adjudication package, and send it to the adjudication office within 6 weeks from occurrence of the event.

After cessation of the study drug, it is at the investigator's discretion to continue with other antithrombotic therapy. The investigator should document this therapy in the eCRF. Thrombotic events will not be reported as adverse events or serious adverse events, as they will be reported as efficacy outcomes, which will be documented in the eCRF.

9.5. Sample Collection and Handling

The actual dates and times of sample collection must be recorded in the eCRF or laboratory requisition form.

If blood samples are collected via an indwelling cannula, an appropriate amount (eg, 1 mL) of fluid slightly greater than the dead space volume of the lock will be removed from the cannula before each blood sample is taken. If a blood sample is taken from a central line, at least 3 mL of blood should be withdrawn prior to collecting study blood samples. Investigators should follow their institution's policy for discarding or re-infusing withdrawn blood. Heparin can be used to maintain catheter patency; however, before collecting PK/PD samples, the catheter needs to be flushed with saline and the first volume of (diluted) blood should be withdrawn, as described above.

Refer to the Time and Events Schedule for the timing and frequency of all sample collections.

Instructions for the collection, handling, storage, and shipment of samples are found in the laboratory manual that will be provided. Collection, handling, storage, and shipment of samples must be under the specified, and where applicable, controlled temperature conditions as indicated in the laboratory manual.

9.6. Study Booklet

Parents/legally acceptable representatives will receive a study booklet in Part A and Part B including information on:

- Instructions to return empty study drug packages and unused study drug
- Instructions on signs and symptoms of bleeding
- Instructions on how to report any adverse event occurring within the reporting period.

For the rivaroxaban treatment group:

- Rivaroxaban will be provided in a glass bottle with a child-resistant screw cap. An adaptor and a dosing pipette will be provided to support drug administration. Rivaroxaban should be stored according to the label.

For the ASA group:

- Acetylsalicylic acid will be provided in child-resistant packaging. The ASA tablets should be stored according to the local approved product label.

9.7. Committees

9.7.1. Executive Committee

The EC will provide overall academic leadership for the study and will oversee the conduct of the study and the publication of the results. In addition, the EC will receive recommendations from the IDMC and SC regarding modifications to the study and will decide whether to accept the recommendations. The EC will have 2 co-chairs and will consist of members of academic institutions and 1 member from the sponsor.

9.7.2. Independent Data Monitoring Committee

The IDMC will evaluate PK, PD, safety and efficacy data to ensure subject safety throughout the study. The IDMC will be an independent expert advisory group external to the sponsor and study. For Part A only, the IDMC will review the cumulative data from the Initial PK, PD, and Safety Assessment Period and will provide the recommendation to the EC and Sponsor Committee to cease enrollment in Part A and to start enrollment directly into Part B. The IDMC will operate for both Part A and Part B. The decision tree of rivaroxaban exposure acceptability criteria will be described in the IDMC charter.

9.7.3. Data Review Committee

The DRC consists of members from the sponsor not directly involved in the conduct of the study, who will evaluate the PK and safety of each subject in Part A, and who will evaluate that information relative to the PBPK model predictions. The DRC will assess before the subject returns for Day 12 Visit the PK, PD, and the safety data available from each subject, prior to the subject continuing in the study to complete the planned 12 months of open-label rivaroxaban therapy. The DRC will only operate during Part A.

9.7.4. Central Independent Adjudication Committee

The CIAC is comprised of specialist physicians as appropriate and necessary. Committee members do not directly enroll subjects in the study, are not involved in the study monitoring, and do not have direct operational responsibilities for the conduct of the study. Members will review all safety and efficacy outcomes that occur post-enrollment as they become available and adjudicate and classify the following events in a consistent and unbiased manner according to definitions in the CIAC charter while blinded to treatment assignment:

Safety and efficacy outcomes include bleeding events, any thrombotic event (venous or arterial), other vascular events as listed in Section 9.4, and deaths that occur during the study and the 30-day post study treatment period.

The CIAC procedures will be described in the CIAC charter. Adjudication results will be the basis for the final analyses.

9.7.5. Steering Committee

The SC will advise and assist the EC with regard to the scientific and operational aspects of the study. Details of the composition, roles, and responsibilities will be documented in the SC charter.

9.7.6. Sponsor Committee

The Sponsor Committee is responsible for communicating the IDMC recommendations within the Sponsor and identifying appropriate actions based on the recommendations of the IDMC.

10. SUBJECT COMPLETION/WITHDRAWAL

10.1. Completion

A subject will be considered to have completed the study if the subject completes:

- The Follow-Up Contact 30 days after the last dose of study drug taken for subjects who complete the 12 month treatment
- The ESMD Month 12 Follow-Up for subjects who discontinue the study drug prematurely

10.2. Discontinuation of Study Drug

If a subject's study drug must be discontinued before the end of the treatment regimen, this will not result in automatic withdrawal of the subject from the study.

10.2.1. Temporary Discontinuation of Study Drug

Study drug may be temporarily discontinued if the subject:

- Undergoes any surgical procedure, or has a medical condition that may require temporary interruption of the study drug, or use of prohibited therapy due to bleeding risk, or use of other antiplatelet or anticoagulant therapy
- Experiences a significant bleeding event
- Develops a platelet count $<50,000/\mu\text{L}$
- Has any serious adverse event possibly related to or exacerbated by study drug administration
- Requires a prohibited therapy on a temporary basis (see Section 8, Prestudy and Concomitant Therapy)

The investigator should consider stopping the study drug in pediatric subjects with elevated ALT values $>5 \times \text{ULN}$ and are increasing, or if ALT values remain unchanged at $>5 \times \text{ULN}$ with no change in total bilirubin for more than 2 weeks and are considered clinically relevant. In addition, investigators should also terminate the study drug in children with worsening clinical symptoms of liver injury and no other acceptable explanation.

The study drug can be resumed at any time when in the opinion of the investigator it is safe to do so. Otherwise the subject will be permanently discontinued from study drug.

10.2.2. Permanent Discontinuation of Study Drug

A subject's study treatment should be discontinued permanently if:

- The investigator believes that for safety reasons (eg, adverse event or persistent noncompliance) it is in the best interest of the subject to discontinue study treatment
- The subject has a thrombotic event
- The subject develops any condition that requires treatment with anticoagulant or antiplatelet therapy
- The subject has a major bleeding event, eg, intracranial bleeding (for definitions of major bleeding see Section 9.3.1, Bleeding Events)
- The subject, his or her parents/legally acceptable representatives request to discontinue the study drug permanently

For subjects in Part A and Part B who prematurely and permanently discontinue the study drug for any reason, the ESMD visit will be performed as soon as possible after discontinuation of the study drug. A Follow-Up phone contact will be performed 30 days following the last dose of the study drug. In addition, an ESMD Month 12 Follow-Up phone contact will be conducted at the end of the planned treatment period. This excludes subjects who are enrolled after local reading of the Screening transthoracic echocardiogram rules out thrombosis, and subsequently reported to have thrombosis after central reading by the core laboratory of the same transthoracic echocardiogram. These subjects will be withdrawn from the study when the result of the echocardiogram by the core laboratory becomes available. Subjects will be asked to return for

the ESMD visit as soon as possible. They will not be required to have a repeat transthoracic echocardiogram as part of the ESMD. Subjects will go on to receive proper care according to the healthcare provider's judgment. They will be contacted by phone approximately 30 days (+/- 7 days) after last dose of study drug (Follow-Up Contact). An ESMD Month 12 follow up visit will not be required.

10.3. Withdrawal from the Study

A subject will be withdrawn from the study for any of the following reasons:

- Lost to follow-up
- Withdrawal of consent/assent
- An internal DRC considers that the subject should not continue rivaroxaban treatment after the Initial PK, PD and Safety Assessment Period
- The core laboratory reports a thrombosis on the same Screening transthoracic echocardiogram that was ruled out by the local reader.
- Other – eg, termination of the study by the sponsor, closing of study sites

When a subject withdraws before completing the study, the reason for withdrawal is to be documented in the eCRF and in the source document. Study drug assigned to the withdrawn subject may not be assigned to another subject.

If a subject is withdrawn before the end of the study for reasons other than being lost to follow-up, the ESMD assessments should be obtained as soon as possible and a Follow-up phone contact will be performed approximately 30 days (+/-7 days) after last dose of study drug. This excludes subjects withdrawn after central reading by the core lab reports a thrombosis on Screening transthoracic echocardiogram. See Section 10.2, Discontinuation of Study Drug for more details.

If a subject is lost to follow-up, every reasonable effort must be made by the study site personnel to contact the subject and determine the reason for discontinuation/withdrawal. The measures taken to follow up must be documented.

Subjects who withdraw will not be replaced.

If a subject is unwilling or unable to return for follow-up visits in person or have follow-up contacts, the sites should collect as much follow-up visit information as possible, including contacting the subject or the subject's representative or health care professional, by telephone or by mail, to determine vital status and if an endpoint event has occurred, as agreed to by the subject and/or the subject's representative during the initial informed consent process. If applicable, vital status may be obtained by reviewing the subject's medical or public records unless this process is not allowed by local regulations.

11. STATISTICAL METHODS

Statistical analysis will be done by the sponsor or under the authority of the sponsor. A general description of the statistical methods to be used to analyze the PK, PK/PD, safety, and the efficacy data is outlined below. Specific details will be provided in the Statistical Analysis Plan (SAP), including, if necessary, censoring rules for time-to-event analyses and imputation rules for missing or partially missing dates.

The SAP will be finalized prior to first subject enrolled in the study.

Data from subjects participating in Part A of the study are planned to be combined with data from subjects in Part B of the study who were randomized to rivaroxaban. Summaries will also be provided based on data from: (a) randomized subjects only (rivaroxaban vs. ASA) from Part B, and (b) subjects participating in Part A only.

For both parts of the study, safety and efficacy results (adverse events, bleedings, and thrombotic events) will be summarized. All summaries will be presented using appropriate descriptive statistics for study variables including demographic and baseline characteristics. Descriptive statistics such as mean, median, standard deviation, minimum, and maximum will be used to summarize continuous variables. Counts and percentages will be used to summarize categorical variables.

The best available data for safety events will be used by the DRC and IDMC to review subjects in the Initial PK, PD, and Safety Assessment Period of Part A. The CIAC-adjudicated results will be used in the final analysis for all subjects.

No statistical hypothesis will be tested in this study.

11.1. Analysis Populations and Periods

11.1.1. Subject Information

Each summary or analysis involves the following 2 aspects: 1) analysis set, specifying the subjects to be included; and 2) analysis period, specifying the time window within which data will be included.

Key analysis sets and analysis periods are defined below.

11.1.2. Analysis Sets

Full Analysis Set: This analysis set consists of all subjects in Part A who receive at least 1 dose of study drug and all subjects in Part B who complete randomization and receive at least 1 dose of study drug.

Safety Analysis Set: This is the same as Full Analysis Set.

PK Analysis Set: All subjects who received at least 1 dose of study drug and have quantifiable rivaroxaban plasma concentrations will be included in the descriptive PK analysis.

PD Analysis Set: All subjects who received at least 1 dose of study drug and have quantifiable PT, aPTT, and anti-FXa activity values will be included in the descriptive PD analysis.

11.1.3. Analysis Periods

On-Treatment Period: This analysis period includes all data from the first dose of study drug to 2 days after the last dose of the study drug administration (inclusive).

Up-to-End-of-Treatment Period: This analysis period includes all data from first dose to end of treatment visit (Month 12 or ESMD visit).

11.2. Sample Size Determination

A total of at least 100 pediatric subjects overall are planned to be enrolled in this study. Due to the limited availability of the study population and the expected low event rates, this study is not powered to test a formal hypothesis for efficacy. The total sample size is based on regulatory feedback to obtain sufficient safety data in this pediatric population.

The sample size of approximately 10 subjects for Part A is considered adequate for the initial assessment of the rivaroxaban PK in the studied pediatric subjects. Approximately 90 subjects will be enrolled into Part B of the study.

11.3. Pharmacokinetics/Pharmacodynamics Analyses

Descriptive statistics will be used to summarize rivaroxaban PK data for each time interval. Pharmacodynamic measurements, including PT, aPTT, and anti-FXa activity will be plotted against rivaroxaban plasma concentrations and will also be summarized by timepoint.

Rivaroxaban PK parameters including AUC_{0-24} , C_{max} after single dose and AUC_{0-24} , C_{max} , and minimum plasma concentration (C_{min}) at steady state will be derived through model-based methods. The PK/PD relationship will be quantified. Results from PK and PK/PD analyses will be reported separately from the Clinical Study Report. When appropriate, PK and PD data collected in this study may be used for ad hoc meta-analyses to further explore PK/PD relationships of rivaroxaban in pediatric subjects.

11.4. Safety Analyses

All safety analyses will be performed on the Safety Analysis Set (described in Section 11.1.2, Analysis Sets) and by treatment group as received.

Bleeding Events

Bleeding events that occur during the On-Treatment Period will be summarized by treatment group. Bleeding events observed more than 2 days after stopping the study drug will be summarized separately. Individual listings of major and clinically relevant non-major bleeding events will be provided. The bleeding events will be adjudicated by the CIAC.

Cumulative incidences and incidence rates over time based on time to the first bleeding event will be provided by treatment group using the Kaplan-Meier method.

Adverse Events

Overall safety will also be assessed by summarizing adverse events by treatment group.

The verbatim terms used in the eCRF by investigators to identify adverse events will be coded using the Medical Dictionary for Regulatory Activities (MedDRA). Treatment-emergent adverse events are adverse events with onset during the treatment period or that are a consequence of a pre-existing condition that has worsened since baseline. All reported adverse events will be included in the analysis. For each adverse event, the percentage of subjects who experience at least 1 occurrence of the given event will be summarized by treatment group. In addition, comparisons between treatment groups will be provided if appropriate.

Individual listings of adverse events (including treatment group, age, weight, height, gender, adverse event as reported, start, duration, severity, and relationship to the study drug) will be provided. The incidence of treatment-emergent adverse events will be summarized by treatment using MedDRA preferred terms grouped by primary system organ class.

Summaries, listings, datasets, or subject narratives may be provided, as appropriate, for those subjects who die, who discontinue treatment due to an adverse event, or who experience a severe or a serious adverse event. Additional summaries, listings, or subject narratives may be provided, as appropriate.

Clinical Laboratory Tests

This study will collect laboratory data at the timepoints specified in the Time and Events Schedule. Laboratory data will be summarized by treatment group.

11.5. Efficacy Analysis

Efficacy analyses will be performed on the Full Analysis Set, excluding subjects who start on study drug but are discontinued if central reading by the core laboratory reports thrombosis on the Screening transthoracic echocardiogram. These subjects will be included however in the safety analysis. Thrombotic events that occur during the Up-to-End-of-Treatment Period will be summarized by treatment received. Events that occur after Up-to-End-of-Treatment Period (after Month 12 or ESMD visit) will be summarized separately.

The efficacy outcomes will be adjudicated by CIAC.

The numbers and percentages of subjects with missing Follow-Up Contact (30-days after last dose) will be summarized. Details will be provided in the SAP.

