- i) Minimum criteria for the availability of documentation supporting the eligibility criteria are described in Section 17.4, Source Documentation. Check clinical status again before first dose of study medication.
- j) Subjects will be enrolled and randomized on Visit 2/Day 1 after meeting inclusion and exclusion criteria. Subjects may be enrolled and randomized on the business day prior to Day 1 to facilitate logistics provided the investigator ensures that the subject meets all eligibility criteria prior to randomization. The first dose of study drug will be administered on site on Day 1 if the subject is still eligible.
- k) For subjects randomized to rivaroxaban, the AM dose will be administered at the site.
- l) If a suspected outcome event (thrombotic or bleeding event) occurs, the adjudication package is to be completed.
- m) Only vital status and thrombotic events (no bleeding events) will be assessed and an adjudication package will be completed.
- n) Adverse event assessment includes a review of all ongoing and new adverse events since the last visit for all visits through Month 12.
- o) Physical examination of the subject will be symptom-driven.
- p) Transthoracic echocardiograms will be obtained at screening, Month 6 and Month 12, or ESMD and whenever medically necessary, and results sent to core laboratory. For screening see footnote 'a'.
- q) Hematology (complete blood count [CBC] with differential, platelet count); blood chemistry (liver function tests [alanine aminotransferase, ALT; aspartate aminotransferase, AST; total and direct bilirubin, alkaline phosphatase] and creatinine).
- r) Hematology and serum chemistry testing at screening (testing should be done after the Fontan procedure and results should be available within 21 days prior to randomization, at Month 12 and ESMD visit). Note: Hospital laboratory, local laboratory results or central laboratory results are acceptable at screening, and the most recent clinical laboratory results will be used for screening if there are multiple laboratory results.
- s) If a subject experiences a major bleeding event while being treated with rivaroxaban, obtain PK and PD samples (see also Section 9.3.2 for approach to the subject with a bleeding event and Section 9.5 for sample instructions).
- t) To be collected at any timepoint during the visit (PK, PT, and aPTT). Parent/legally acceptable representative should document timing of the administered AM study drug dose.

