2. OBJECTIVES AND HYPOTHESIS

2.1. Objectives

Primary Objectives

Part A

To characterize the single- and multiple-dose PK and PK/ PD profiles after oral rivaroxaban therapy administered to pediatric subjects 2 to 8 years of age with single ventricle physiology who have completed the Fontan procedure within 4 months prior to enrollment.

Part B

To evaluate the safety and efficacy of rivaroxaban, administered twice daily (exposure matched to rivaroxaban 10 mg once daily in adults) compared to ASA, given once daily (approximately 5 mg/kg) for thromboprophylaxis in pediatric subjects 2 to 8 years of age with single ventricle physiology who have completed the Fontan procedure within 4 months prior to enrollment.

Secondary Objectives

Part A

To assess the safety and tolerability of rivaroxaban treatment.

Part B

To further characterize the PK and PK/PD profiles of rivaroxaban.

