9.1.5. Posttreatment Period (Follow-Up Contact)

In both Part A and Part B, all subjects will be contacted by phone at the following time periods:

1. Subjects who complete the 12-Month treatment period or subjects who are withdrawn from the study will receive 1 phone contact: Approximately 30 days (\pm 7 days) after last dose taken (Follow-Up Contact). A review of safety and efficacy outcomes will be conducted at this contact and any concomitant medications will be recorded.
2. Subjects who permanently discontinue study drug early but continue in (are not withdrawn from) the study will receive 2 phone contacts: Approximately 30 days (\pm 7 days) after last dose taken (Follow-Up Contact) to review safety and efficacy outcomes and any concomitant medications; and at the end of the planned treatment period (ESMD 12 Month follow up) to determine their vital status and thrombotic events (no bleeding events).

Transition at End-of-Treatment

If at the end of study treatment a decision is made to continue a subject on an anticoagulant or ASA, the following guidelines are provided:

- Subjects who switch from rivaroxaban to heparin/LMWH/fondaparinux can switch at the time of the next scheduled dose.

- Subjects who switch from rivaroxaban to VKA need to continue rivaroxaban for 48 hours after the first dose of VKA. After 2 days of co-administration, an INR should be obtained prior to the next scheduled dose of rivaroxaban. Co-administration of rivaroxaban and VKA is advised to continue until the INR is ≥ 2.0 .
- Subjects who switch from rivaroxaban to ASA can switch to ASA at the time of the next scheduled dose.

Any anticoagulant/antiplatelet medication initiated at the end of the study treatment period will be documented on the concomitant medication eCRF page.

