Additionally, data may also be summarized based on Full Analysis Set and up-to-last-FU (last contact) period or Per-protocol Analysis Set and On-treatment period.

Incidence rates (number of subjects with efficacy event during the period divided by number of subjects at risk at the beginning of the period) and the respective 95% CIs will be calculated for the primary efficacy outcome by treatment group.

Cumulative incidences (time to first event; Kaplan-Meier) will also be calculated for the efficacy outcomes.

In addition, listings of any efficacy outcomes will be provided.

Baseline demographics and disease characteristics relationship to thrombotic risk may be explored.

The numbers and percentages of subjects with missing Follow-Up Contact (30-days after last dose or Month 12) will be summarized.

All missing or partial data will be presented in the subject data listing as they are recorded on the eCRF.

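### Part B is set up to compare rivaroxaban with ASA, but the protocol and SAP name no between-arm estimate, word the efficacy grouping in three ways, and leave a joined Month 12 thrombosis count optional

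*Protocol*

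**What the plan says.** **Objective.** Protocol 2.1 gives the Part B primary objective as "To evaluate the safety and efficacy of rivaroxaban, administered twice daily (exposure matched to rivaroxaban 10 mg once daily in adults) compared to ASA". Protocol 3.2 says that randomisation is there to strengthen descriptive comparisons between the arms, and that ASA was chosen so that an antiplatelet and an anticoagulant can be compared descriptively. No hypothesis is tested (Protocol 2.2 and 11; SAP 1.3).

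**Efficacy output.** SAP 5 plans an incidence per arm, "and the respective 95% CIs will be calculated for the primary efficacy outcome by treatment group", and Kaplan-Meier cumulative incidences. Protocol 11 and SAP 2 also promise a summary restricted to randomised Part B children, rivaroxaban versus ASA. SAP 4.1 plans the same kind of per-arm intervals and curves for major bleeding. Protocol 11.4 foresees between-group comparisons for adverse events where appropriate.

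**Grouping.** Protocol 11.5 states: "Thrombotic events that occur during the Up-to-End-of-Treatment Period will be summarized by treatment received". Protocol 11 and SAP 2 form the pooled rivaroxaban group and the Part B summary from children described as randomised. SAP 5 says only treatment group.

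**Time window.** The main efficacy period is defined in Protocol 11.1.3: "This analysis period includes all data from first dose to end of treatment visit (Month 12 or ESMD visit"). Early stoppers who remain in the study are also telephoned at planned Month 12 "to determine their vital status and thrombotic events (no bleeding events") (Protocol 9.1.5). The Part B Time and Events Schedule, footnote m, adds: "Only vital status and thrombotic events (no bleeding events) will be assessed and an adjudication package will be completed". Events after the main period are to be reported separately (Protocol 11.5; SAP 5). A joined count appears only here in SAP 5: "Additionally, data may also be summarized based on Full Analysis Set and up-to-last-FU (last contact) period". By contrast, the completeness of that follow-up is a firm output: "The numbers and percentages of subjects with missing Follow-Up Contact (30-days after last dose or Month 12) will be summarized".

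**The concern.** The randomised comparison is the reason for having Part B, and three choices that shape it are open or worded inconsistently.

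- **Contrast.** Two separate arm intervals do not give the uncertainty of their difference. Readers will subtract the two percentages anyway, and nothing planned tells them how imprecise the result is.
- **Grouping.** Read literally, Protocol 11.5 and the randomisation wording elsewhere can put the same child in different arms. With about 30 ASA children, a single event in such a child is visible in the result.
- **Early stoppers.** No required output gives 12-month cumulative incidence from all the adjudicated events that the study collects. Kaplan-Meier to ESMD fills that gap only if risk is unchanged after stopping. Protocol 10.2.2 lists as one stopping reason a condition needing anticoagulant or antiplatelet treatment, so risk may change. After the 30-day call, the Month 12 contact is the only planned contact that can show whether it did.

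**Working it through.** **Inputs.** About 90 children in Part B (Protocol 11.2) at 2:1 (Protocol 5): 90 × 2/3 = 60 rivaroxaban and 90/3 = 30 ASA. The plan states no event rate, stopping rate or effect for this trial, so there is no planned figure to reproduce. All counts and rates below are assumptions.

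**1. What a contrast would add.** Assume 3/60 versus 3/30.

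- Wilson 95% intervals: rivaroxaban 5.0% (1.7 to 13.7), ASA 10.0% (3.5 to 25.6). This is the kind of output now planned (SAP 5 does not name the interval method).
- Difference: 5.0 - 10.0 = -5.0 points.
- Newcombe limits, from the Wilson limits (l, u):
  - lower = D - √[(p₁-l₁)² + (u₂-p₂)²] = -0.050 - √(0.0329² + 0.1562²) = -0.210
  - upper = D + √[(u₁-p₁)² + (p₂-l₂)²] = -0.050 + √(0.0870² + 0.0654²) = 0.059
- Result: -5.0 points (-21.0 to 5.9). Miettinen-Nurminen gives -21.3 to 5.9.

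**2. Effect of the grouping rule.** Same counts, with one child who takes the other arm's drug:

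| Case | As-received counts | Difference, points (Newcombe 95% CI) | Shift from -5.0 |
|---|---|---|---|
| Assigned ASA, took rivaroxaban, event | 4/61 v 2/29 | -0.3 (-15.9 to 10.1) | +4.7 |
| Assigned ASA, took rivaroxaban, no event | 3/61 v 3/29 | -5.4 (-21.8 to 5.5) | -0.4 |
| Assigned rivaroxaban, took ASA, event | 2/59 v 4/31 | -9.5 (-25.7 to 1.7) | -4.5 |
| Assigned rivaroxaban, took ASA, no event | 3/59 v 3/31 | -4.6 (-20.2 to 6.3) | +0.4 |

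The rule matters only when the wrong-drug child also has an event.

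**3. Stopping the count at ESMD.** Assume a 12-month risk r of 10% or 20% on treatment, and a fraction d of 10% or 30% stopping for non-thrombotic reasons at uniform times over the year. Stopping because of thrombosis is already counted as an event. Let H = -ln(1-r) and let the hazard after stopping be multiplied by m. Kaplan-Meier to ESMD then estimates r. With constant hazard the true 12-month risk among stoppers is

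- m = 2: 1 - e^(-2H)(e^H - 1)/H
- m = ½: 1 - e^(-H/2)(1 - e^(-H/2))/(H/2)

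The Kaplan-Meier error is d × (stoppers' risk - r). For r = 20%, d = 30%, H = 0.2231:

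- Doubling: stoppers' risk = 1 - 0.64 × 0.25/0.2231 = 0.283, so 0.3 × 0.083 = 2.5 points understated.
- Halving: stoppers' risk = 1 - 0.8944 × 0.1056/0.1116 = 0.154, so 0.3 × 0.046 = 1.4 points overstated.

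The front-loaded columns put two-thirds of the hazard in the first 6 months on study. True risk minus Kaplan-Meier, in points:

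| r, d | Doubles, constant | Doubles, front-loaded | Halves, constant | Halves, front-loaded |
|---|---|---|---|---|
| 10%, 10% | 0.46 | 0.38 | -0.24 | -0.20 |
| 10%, 30% | 1.37 | 1.15 | -0.72 | -0.60 |
| 20%, 10% | 0.83 | 0.69 | -0.46 | -0.39 |
| 20%, 30% | 2.49 | 2.08 | -1.39 | -1.16 |

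If stopping is 30% in one arm and 10% in the other, the bias in the difference is the gap between paired rows: 0.8-1.7 points if risk doubles, and 0.4-0.9 in the opposite direction if it halves. The standard error of a 60:30 difference, √[r(1-r)(1/60 + 1/30)], is 6.7 points at 10% and 8.9 at 20%.

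**The case against.** The strongest reply is that this is a descriptive study and does what it says. Part B summaries by arm, intervals and curves are planned, the trial is not powered for efficacy (Protocol 11.2), and anyone can subtract two percentages. An interval for the difference could also be misread as a test: 3/60 versus 6/30 would give -15.0 (Newcombe -32.6 to -1.4), which excludes zero where no test was intended. Table shells are in the separate Data Presentation Specifications (SAP 1), so a contrast may exist there. The caution about misreading stands and belongs in the wording. It does not justify leaving out the interval, because a bare subtraction invites more over-reading than a wide interval does.

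Three stronger readings are tempting, and the documents do not support them.

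- **That efficacy is analysed as received throughout.** Protocol 11 and SAP 2 use randomisation wording for the same summaries, so this is an inconsistency. Wrong-drug cases should be rare because the IWRS assigns the kit (Protocol 5). Taking incorrect study drug is also a key deviation that removes a child from the Per-protocol Set (SAP 2.2), and it is among the deviation categories in SAP 3.6.
- **That events after ESMD are lost.** They must be reported separately; only the joined count is optional. Keeping it secondary is defensible: the ESMD visit includes an echocardiogram, while the Month 12 contact is by telephone and the child may be on other antithrombotics.
- **That Kaplan-Meier to ESMD understates risk.** Further antithrombotic treatment could lower risk after stopping, and then it overstates.

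The front-loading is also only indicative. Protocol 1.1.1 counts the higher early risk from surgery, and enrolment may come up to 4 months later.

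**Conclusion.** The point holds as a low-cost improvement to the plan; no planned result is shown to be wrong. Within these two documents, no between-arm estimate with an interval is specified for thrombotic events or for major bleeding, although Part B's objective compares the arms on both efficacy and safety. The grouping wording conflicts between sections. It would move the difference by 4 to 5 points only in the rare case of a wrong-drug child with an event, under assumed counts of three events per arm. A cumulative thrombosis count that includes events after ESMD is optional, and its period runs to the trial reference end date (SAP 2.3), so for completers it extends past Month 12.

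Under the assumed risks and stopping rates, the Kaplan-Meier error lies between 2.5 points too low and 1.4 points too high, well below sampling error. The gain is a clear, prespecified estimate with its uncertainty, more than the removal of a large bias.

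**What to change.** In Protocol 11.5 and SAP 5, with a matching line in SAP 4.1:

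1. State that the Part B efficacy summary is by assigned arm, in the dosed set and with the existing exclusion for screening thrombus. Keep as-received and pooled Part A plus B versions as supportive. Report the number randomised but not dosed in each arm.
2. Add a Part B risk difference with a Newcombe or Miettinen-Nurminen 95% CI for thrombotic events, labelled descriptive and without a test. Do the same for major bleeding, by treatment received as Protocol 11.4 already plans.
3. Beside the ESMD version, require a summary of CIAC-confirmed thrombotic events to the planned treatment end date of SAP 2.1. It should take in the Month 12 visit (±7 days) or the ESMD Month 12 contact (±14 days), with Kaplan-Meier censoring of withdrawn children at last contact.

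The cost is wording and a few tables, with no new data collection. There are two downsides. The intervals will be wide and must not be read as tests. The extended count mixes events found by telephone with events found by protocol echocardiogram, some of them on other antithrombotics, so it should sit beside the ESMD version and not replace it.
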